## 7. STUDY POPULATION

### 7.1. Subjects Disposition

The following will be summarized in the Subject Disposition table.

- A summary of the number of subjects in each of the analysis populations.
- The number and percentages of subjects who signed informed consent but were not randomized along with the reason for why they failed screening.
- The number and percentage of subjects who were randomized but not treated.
- The count and percentage of subjects who completed or discontinued from the study. For those who discontinued from the study, the primary reason for discontinuation from the study will be presented.

### 7.2. Protocol Deviations

As per ICH E3 guideline Section 10.2, all important deviations related to study inclusion or exclusion criteria, conduct of the trial, patient management or patient assessment will be summarized by site and grouped into different categories, such as:

- those who entered the study even though they did not satisfy the entry criteria;
- those who developed withdrawal criteria during the study but were not withdrawn;
- those who received the wrong treatment or incorrect dose;
- those who received an excluded concomitant treatment.

Additional details of reviewing and classifying protocol deviations as important are detailed in the protocol deviation handling plan.

Final categorization of protocol deviations will be done prior to database lock and unblinding and documented.

In Appendix 16.2.2, individual patients with these protocol deviations will be listed,

### 7.3. Demographic and Baseline Characteristics

The demographic and Baseline characteristics data collected at the Screening Visit (V1) will be presented for the Safety populations. The continuous variables, i.e. age in years, height in meters, weight in kilograms, Body Mass Index (BMI) in  $\text{kg/m}^2$ , baseline ALSFRS-R and SVC (% predicted) score, time since ALS diagnosis in months, and time since ALS first symptom in months will be summarized using descriptive statistics (n (missing), mean, SD, Q1, median, Q3, minimum, and maximum). The discrete variables, i.e. gender, ethnicity, race, and El Escorial Criteria and ALSFRS-R  $< 35$  vs  $\geq 35$  will be summarized using counts and percentages.

## 7.4. Subject Inclusion and Exclusion Criteria

Reasons for screen failure including Inclusion and exclusion criteria not met prior to randomization will be listed for each subject.

## 7.5. Medical History and Medical Conditions Present at Entry

Medical history will be coded using the MedDRA, version 20.1. Counts and percentages of subjects with each medical history will be summarized using MedDRA system organ class (SOC) and preferred term (Preferred Term) for the Safety population. System organ classes will be ordered alphabetically and preferred terms within system organ classes will be ordered by descending incidence of all subjects.

## 7.6. Prior Medication History and Concomitant Medications

Prior medications are defined as those taken and stopped prior to the date of first transplantation. Any medication given at least once on or after the date of first transplantation will be defined as a concomitant medication including those which were started before the date of first transplantation and continued after it. Concomitant medications will be coded using the WHODD, to identify the drug class and preferred drug name. Anatomical Therapeutic Chemical drug class 1 will be used. Preferred name will be derived from the active ingredient list for each drug; in cases where more than 3 ingredients are listed, the drug name will be used as the preferred name.

Counts and percentages of prior, as well as concomitant medications will be summarized by drug class and preferred name for the Safety population. Changes in concomitant medications will be summarized.

## 7.7. Pregnancy Test

Pregnancy test results will be listed by subject.

# 8. EFFICACY

## 8.1. General Considerations

Descriptive statistics for continuous and categorical variables will be presented as described in [Section 6.4](#).

Each statistical test will be performed at Type I error  $\alpha=0.05$  (Two-sided).

## 8.2. Multiple Comparisons and Multiplicity

The primary efficacy endpoint and key secondary efficacy endpoints will be tested sequentially to account for multiplicity and preserve overall Type I error. No adjustments will be made for multiple comparisons in testing other secondary or exploratory efficacy endpoints.

## 8.3. Analysis of the Primary Efficacy Endpoint

### 8.3.1. Primary Efficacy Analysis

The primary efficacy endpoint is based upon the ALSFRS-R which is a validated scale based upon 12 items, each rated from 0 to 4. Scores of 4 are Normal and 0 are the worst. Note the ALSFRS-R total score is between 0 and 48. The slope is determined by fitting a linear regression using all assessments between the time points mentioned.

A subject is defined as a responder if his/her rate of disease progression as measured by the ALSFRS-R slope (rate of decline per month fit using linear regression) over 28 weeks from baseline improves by  $\geq 1.25$  points/month as compared to the disease progression over the pre-treatment period. All deaths related to disease progression will be defined as non-responders.

The pre-transplantation slope in ALSFRS-R score per month is calculated using all available ALSFRS-R scores from the screening visit through the last pre-transplantation visit (including the assessment pre-transplantation at the baseline first transplantation visit). The post-transplantation slope through any post-transplantation visit is calculated from the baseline visit (last available ALSFRS-R prior to and inclusive of the transplantation visit) through each post-transplantation visit (using all available ALSFRS-R scores post baseline).

The above slopes are computed by fitting a linear regression on ALSFRS-R scores as the dependent variable and days as the independent variable. The slope from the linear regression is a change in ALSFRS-R score per day. This is converted to a change in ALSFRS-R score slope per month by multiplying the slope by 30.4375 [365.25/12] to obtain a slope per month (Change in ALSFRS-R score per month).

The null and alternative hypothesis are as follows:

$$H_0: P_t = P_p$$

$$H_a: P_t \neq P_p$$

Where  $H_0$  and  $H_a$  are the null and alternative hypothesis respectively and  $P_t$  and  $P_p$  are the proportion of participants in the treated group and placebo group whose post-treatment slope over 28 weeks from baseline as compared to the pre-treatment slope in the overall ALSFRS-R score improves by  $\geq 1.25$  points/month.

The hypothesis testing to compare the percentage of responders between the two treatment groups will be based upon the mITT population, using logistic regression adjusting for covariates as indicated below under independent variables in the model. If logistic regression cannot be appropriately fit based upon the distribution of covariates between treatment groups a Chi-squared test will be used to test the above null hypothesis.

The dependent variable for logistic regression will be whether a subject is a responder or not as described above. The independent variables in the model will be treatment group, baseline ALSFRS-R score, duration from onset of symptoms to first treatment, site of onset (Limb vs Bulbar & Limb), Riluzole use, and ALSFRS-R slope pre-treatment.

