
Efficacy
	
The primary efficacy endpoint is based upon the ALSFRS-R functional rating scale which is a validated scale based upon 12 items, each rated from 0 to 4. Scores of 4 are Normal and 0 are the worst. Note the ALSFRS-R overall total score is between 0 and 48. The slope is determined by fitting a linear regression using all assessments between the time points mentioned.
 
The primary efficacy endpoint will be the proportion of participants with a ≥ 1.25 point/month improvement in post-treatment slope vs. pre-treatment slope in ALSFRS-R score at 28 weeks from the first treatment.
 
The primary and secondary efficacy endpoints will be analyzed using the ITT population which will be defined as all subjects randomized.
 
The modified intent to treat (mITT) population will be defined in this study as all participants who were randomized, treated and have at least three ALSFRS-R assessments: one pre-treatment assessments of ALSFRS-R prior to the baseline assessment, a baseline assessment and one post-treatment assessment. Baseline will be the ALSFRS-R assessment at the first transplantation visit (Week 0, Visit 6 in the Study scheme) prior to treatment. This will permit computing the slope from a linear regression pre- and post-treatment to get a rate of decline in ALSFRS-R per month pre-treatment and post- treatment.
 
No to minimal differences are expected between the mITT and ITT populations, however if there are differences, analysis of the primary endpoint and other select efficacy analyses will also be generated using the mITT population.
 
The ITT and mITT population will be analyzed based upon the treatment groups subjects are randomized to.
 
Supporting efficacy analyses will be conducted using the Efficacy Evaluable (EE) population which will be a subset of the mITT population. The exact criteria used to define the EE population will be finalized prior to locking the database and unblinding the study.
 
Each statistical test will be performed at Type I error $\alpha=0.05$ (Two-sided). The primary and key secondary efficacy endpoints will be tested sequentially to account for multiplicity and preserve overall Type I error. No adjustments will be made for multiple comparisons in testing additional secondary exploratory efficacy endpoints.
 
A subject is defined as a responder if his/her rate of disease progression as measured by the ALSFRS-R slope (rate of decline per month fit using linear regression) over 28 weeks from baseline improves by ≥ 1.25 points/month as compared to the disease progression over the pre-

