1.9.3.3. Analysis Population

The primary, secondary and exploratory efficacy endpoints will be analyzed using the ITT population which will be defined as all subjects randomized.

The modified intent to treat (mITT) population will be defined in this study as all participants who were randomized, treated and have at least three ALSFRS-R assessments: one pre-treatment assessments of ALSFRS-R prior to the baseline assessment, a baseline assessment and one post-treatment assessment. Baseline will be the ALSFRS-R assessment at the first transplantation visit (Week 0, Visit 6) prior to treatment. This will permit computing the slope from a linear regression pre- and post-treatment to get a rate of change in ALSFRS-R per month pre-treatment and post-treatment.

No to minimal differences are expected between the mITT and ITT populations, however if there are differences, analysis of the primary endpoint and other select efficacy analyses will also be generated using the mITT population.

The ITT and mITT populations will be analyzed based upon the treatment groups subjects are randomized to.

Supporting efficacy analyses will be conducted using the Efficacy Evaluable (EE) population which will be a subset of the mITT population. The exact criteria used to define the EE population will be finalized prior to locking the database and unblinding the study.

All safety analyses will be conducted on the Safety Population, which will be defined as all participants who were randomized and had at least one transplantation performed.

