1.9.3.4. Efficacy Analyses

Each statistical test will be performed at Type I error $\alpha=0.05$ (Two-sided). The primary and key secondary efficacy endpoints will be tested sequentially to account for multiplicity and preserve overall Type I error. No adjustments will be made for multiple comparisons in testing additional secondary exploratory efficacy endpoints.

The primary efficacy endpoint is based upon the ALSFRS-R which is a validated scale based upon 12 items, each rated from 0 to 4. Scores of 4 are Normal and 0 are the worst. Note the

ALSFRS-R score is between 0 and 48. The slope is determined by fitting a linear regression using all assessments between the time points mentioned.

A subject is defined as a responder if his/her rate of disease progression as measured by the ALSFRS-R slope (rate of decline per month fit using linear regression) over 28 weeks from baseline improves by ≥ 1.25 points/month as compared to the disease progression over the pre-treatment period. All deaths related to disease progression will be defined as non-responders.

The null and alternative hypothesis are as follows:

$$H_0: P_t = P_p$$

$$H_a: P_t \neq P_p$$

Where H_0 and H_a are the null and alternative hypothesis respectively and P_t and P_p are the proportion of participants in the treated group and placebo group whose post-treatment slope over 28 weeks from baseline as compared to the pre-treatment slope in the overall ALSFRS-R score improves by ≥ 1.25 points/month.

The hypothesis testing to compare the percentage of responders between the two treatment groups will be based upon the ITT population, using logistic regression adjusting for site, and ALSFRS-R slope pre-treatment. Other explanatory variables may be added to the logistic regression model which will be finalized and described in the SAP prior to locking the database and unblinding the study.

The first key secondary endpoint to be tested if the null hypothesis for the primary endpoint is rejected is a comparison between the NurOwn® (MSC-NTF cells) and placebo group of the percentage of participants whose post-treatment slope in the overall ALSFRS-R score as compared to their pre-treatment slope improves by $\geq 100\%$. Note, an improvement of 100% or more indicates achieving a post-treatment slope of ≥ 0 , which means halt or improvement in disease progression as measured by the ALSFRS-R.

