If the null hypothesis for the first key secondary endpoint is rejected, the second key secondary endpoint will be the comparison in change from baseline to Week 28 in ALSFRS-R.

Additional supportive endpoints will include comparison between treatment groups of (a) survival or time to tracheostomy; (b) mean change in slope of ALSFRS-R score over each post baseline visit and the entire follow-up period (2 – 28 weeks) as compared to pre-treatment slope and (c) the change from baseline in ALSFRS-R score to each post baseline time point.

Two sensitivity analyses will be performed using multiple imputations with unobserved data imputed prior to fitting the linear regression. In both sensitivity analyses, the method of multiple imputations (MI) ([Ratitch et al 2013](#)) using Pattern Mixture Model ([Little 1996](#)) will be used. An ALSFRS-R overall score will be considered to be non-missing if at least 6 out of the 12 items were assessed and have valid ALSFRS-R scores. Based upon prior trials the amount of non-monotone missing data are expected to be minimal and hence any non-monotone missing ALSFRS-R scores will be imputed using the Markov Chain Monte-Carlo method. The COVID-19 pandemic may result in additional missed visits resulting in a greater amount of non-monotone or monotone missing data. As per ICH E9, during blinded data review prior to database lock other imputations may be considered. These will be documented in an Amendment to the SAP prior to locking the database and unblinding the study. The method of

multiple imputations uses SAS PROC MI and MIANALYZE to generate multiple complete datasets and combine the results from them.

In the first sensitivity analysis, an assumption of Missing at Random (MAR) will be made and subject's missing data will be imputed using those with available data within the treatment group they were assigned to. In the second sensitivity analysis, an assumption of Missing Not at Random (MNAR) will be made based upon an approach similar to above using multiple imputations with missing data for subject imputed using the available data for Placebo participants.

The analysis for ALSFRS-R subscales will employ a similar approach as described for the primary and secondary efficacy analyses.

Details of all statistical analyses will be provided in the SAP, which will be finalized prior to database lock and unblinding the study.

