### **6.5.2. Modified Intent to Treat (mITT) Population**

All efficacy analyses will be conducted using the mITT population which is defined as all subjects randomized, treated and having an assessment of pre-transplantation slope and post-transplantation slope, which requires at least three ALSFRS-R assessments: one pre-treatment ALSFRS-R assessment prior to the baseline assessment, a baseline assessment and one post-treatment assessment. Baseline will be the ALSFRS-R assessment at the first transplantation visit (Week 0, Visit 6) prior to treatment, or if this is unavailable, the most recent ALSFRS-R assessment prior to this time point. This will permit computing the slope from a linear regression pre- and post-treatment to get a rate of change in ALSFRS-R per month pre-treatment and post-treatment. The mITT population will be analyzed based upon the treatment groups subjects are randomized to. All efficacy analyses will be generated using the mITT population.

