### 8.4. Analysis of key Secondary Efficacy Endpoints

All analyses of the key secondary efficacy endpoints will be performed using the mITT population.

The first key secondary efficacy endpoint is to evaluate the efficacy of NurOwn® (MSC-NTF cells) vs. placebo as measured by the proportion of participants whose disease progression is halted or improved as measured by a 100% or greater improvement in post-treatment slope vs. pre-treatment slope in ALSFRS-R score at 28 weeks following the first treatment. Note, an improvement of 100% or greater means halt or improvement in disease progression (post-treatment slope) as measured by the ALSFRS-R. As in the analysis of the primary endpoint, all deaths due to disease progression will be considered as non-responders. If pre-treatment slope is 0, the % change in post-treatment slope compared to pre-treatment slope will be considered missing. The impact of this will be explored through a sensitivity analysis defined below.

Each subject's pre- and post-transplantation slope, change and percent change in slope will be calculated and listed for each post baseline timepoint.

Percentage change in slope through Week x =  $100 * ([\text{post-transplantation slope through Week x} - \text{pre-transplantation slope from screening through baseline}] / \text{Absolute Value} [\text{pre-transplantation slope from screening through baseline}])$ . Note, the absolute value is taken in the denominator since the pre-transplantation slope is often negative.

The hypothesis testing for the first secondary endpoint of percentage change in slope at 28 weeks following first treatment will follow the same methodology as the primary endpoint described above.

Since percentage change in post-treatment slope as compared to pre-treatment slope is considered missing when the pre-treatment slope is 0, and can be very large for very small values of pre-treatment slope, a sensitive analysis will be performed considering all subjects with post-treatment slope  $\geq 0$  as responders and all deaths due to disease progression as non-responders.

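### The protocol makes all randomised participants (ITT) the confirmatory population; the SAP moves the primary test and every key secondary to mITT, which leaves out anyone never treated

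*SAP*

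**What the plan says.** Protocol. The synopsis states: "The primary and secondary efficacy endpoints will be analyzed using the ITT population which will be defined as all subjects randomized". Section 1.9.3.3 repeats this more broadly: "The primary, secondary and exploratory efficacy endpoints will be analyzed using the ITT population". Section 1.9.3.4 says the comparison of responders between the two treatment "groups will be based upon the ITT population, using logistic regression adjusting for site, and ALSFRS-R slope pre-treatment". mITT is to be run in addition, for the primary endpoint and selected others, if the two sets differ; the stated expectation is "No to minimal differences are expected between the mITT and ITT populations". Among the secondary endpoints so covered is the ALSFRS-R change: "the second key secondary endpoint will be the comparison in change from baseline to Week 28 in ALSFRS-R".

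SAP. Section 8.3.1 says the primary test "will be based upon the mITT population, using logistic regression adjusting for covariates as indicated below". Section 8.4 adds: "All analyses of the key secondary efficacy endpoints will be performed using the mITT population". Section 6.5.2 defines mITT as "all subjects randomized, treated and having an assessment of pre-transplantation slope and post-transplantation slope", which takes at least three ALSFRS-R assessments, one of them after treatment. ITT remains in Section 6.5.3 as an additional analysis of the primary endpoint. Section 8.3.2 lists it as a sensitivity analysis under MAR, with imputation from the assigned arm. The placebo-based MNAR analysis in the same section is not stated to use ITT. No ITT analysis of a key secondary appears in the text available.

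The SAP introduction says the final version reflects FDA feedback but does not tie this to the analysis population. Parts of the SAP are withheld or not shown, including the body of Section 8.6, so a stated reason cannot be ruled out.

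**The concern.** The two governing documents name different confirmatory populations for the same test. The protocol leaves extra covariates and the efficacy-evaluable criteria to the SAP, but not this choice. Testing is sequential, so the whole key-secondary sequence depends on the primary result.

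The population also matters because of the timing. Participants are randomised at Visit 4, about a week before marrow aspiration (Protocol 1.3.4). Isolation and expansion of cells are described for the treatment group only (Protocol synopsis and 1.3.1; SAP 4.1). Participants may go untreated if their cells do not grow (Protocol 1.3.1 and 1.8.5.2). mITT would then drop randomised NurOwn participants for a reason that has no counterpart on placebo. The one ITT analysis that is kept does not meet this point, because own-arm imputation gives never-treated NurOwn participants outcomes drawn from treated ones.

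**Working it through.** **Inputs.** Two-sided alpha 0.05, 90% power, 35% against 15% responders, 97 per arm required and about 100 per arm randomised (Protocol 1.9.3.1; SAP 4.3). Neither document gives an exclusion rate. I assume that a share f = 5% or 10% of NurOwn participants is untreated, and none on placebo.

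**1. The plan's sample size.** n = [1.960·√(2·0.25·0.75) + 1.2816·√(0.35·0.65 + 0.15·0.85)]² / 0.20² = (1.2002 + 0.7636)² / 0.04 = 96.4, so 97 per arm. This matches the plan.

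**2. What selective exclusion could do under the null.** The true rate is 15% in both arms. NurOwn has 100(1 − f) participants in mITT and placebo has 100. The chance of a false NurOwn win is 1 − Φ[(1.96·SE₀ − (p − 0.15)) / SE₁], where p is the NurOwn rate in mITT, SE₀ is pooled and SE₁ unpooled.

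- No excluded participant would have responded, f = 5%: p = 15/95 = 15.8% (+0.8 points). (0.1013 − 0.0079)/0.0517 = 1.81, giving 3.5%.
- The same, f = 10%: p = 15/90 = 16.7% (+1.7 points). (0.1038 − 0.0167)/0.0531 = 1.64, giving 5.0%.
- Exclusion unrelated to outcome: p = 15%, giving 2.5% at either f.
- Every excluded participant would have responded: p = 10/95 = 10.5% or 5/90 = 5.6% (4.5 or 9.4 points too low), giving 0.2% or under 0.1%.

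**3. What ITT costs in power.** With 100 per arm and 15% on placebo, power is Φ[(d − 1.96·SE₀)/SE₁], where d is the difference in rates.

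- If 35% is the rate in all randomised: (0.2000 − 0.1200)/0.0596 = 1.34, giving 91%.
- If 35% applies to treated participants only and the untreated count as non-responders, f = 5%: rate 0.95·35% = 33.25%. (0.1825 − 0.1186)/0.0591 = 1.08, giving 86%.
- The same, f = 10%: rate 0.90·35% = 31.5%. (0.1650 − 0.1171)/0.0586 = 0.82, giving 79%.

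The first reading fits the plan better, because the sample size text says that the assumed rates already allow for discontinuations.

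**The case against.** The strongest reply is that the switch may change little. The protocol expects the two sets to be almost the same. Its own ITT test gives no outcome rule for a participant without a post-treatment slope: only progression-related deaths are non-responders by definition, and imputation appears only as sensitivity analysis. Read literally, an untreated participant could drop out of the protocol's regression as well. This stands. A reader might infer that the two documents must produce different confirmatory p-values because of the population, but that follows only if some randomised participants fall outside mITT and ITT gives them an outcome. The p-values may differ anyway, since the protocol adjusts for site and the SAP does not.

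A reader might also infer that mITT favours NurOwn. The documents do not support that. They give no failure rate, and nothing links cell growth to response. Exclusions for other reasons can occur in both arms. Even in the adverse case above, two-sided error is 5.3% or 6.2% (upper plus lower tail: 3.5 + 1.7 and 5.0 + 1.2). That growth failure affects NurOwn alone is itself an inference: Protocol 1.8.5.2 names no arm.

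Lastly, the pre-treatment SVC slope and survival time counted from baseline might look like SAP errors, because neither is defined for an untreated participant. They are not errors: the SAP runs those analyses in mITT, where everyone was treated. They need attention only once ITT is restored.

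None of this reconciles the two documents. SAP 6.5 allows populations to be modified before unblinding, and SAP 7.1 tabulates participants randomised but not treated. Neither says which population is confirmatory.

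**Conclusion.** The contradiction stands on the text and should be settled before unblinding: ITT is confirmatory in the protocol, mITT in the SAP, with no reason given in the text available. The SAP's choice allows a post-randomisation exclusion that may differ by arm. The size and direction of any bias are unknown. The range in the working, from under 0.1% to 5.0% for a false NurOwn win against a nominal 2.5%, rests on assumed exclusion of 5% or 10% in one arm and on extreme assumptions about who is excluded. If the protocol is right that the sets hardly differ, restoring ITT costs almost nothing; if it is wrong, ITT is needed.

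**What to change.** Before unblinding:

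1. In SAP 6.5.2, 6.5.3, 8.3.1 and 8.4, make ITT, as randomised, the confirmatory population for the primary endpoint and the key-secondary sequence, with mITT supportive. If mITT was deliberate, amend the protocol and give the reason.
2. In SAP 8.3.1, state one rule for a randomised participant with no post-treatment slope. Counting them as non-responders is simplest, since it needs neither a slope nor a Week 0. If placebo-based imputation is used instead, define a Week 0 for untreated participants, because the post-treatment slope starts at the first-transplantation baseline. Own-arm MAR should not be the only ITT analysis.
3. In SAP 8.3.2, state that the placebo-based MNAR analysis is run in ITT.
4. Replace the covariate for time from symptom onset to first treatment with time to randomisation, so that it exists for everyone. If the pre-treatment slope stays as a covariate, say which visits supply it for someone with no Visit 6. Do not use that participant's Visit 1 to Visit 4 slope to define response. Entry requires a decline of at least 3 points in the 12 weeks before randomisation, which selects that slope for steepness and would create responders by chance.
5. State how untreated participants enter each key-secondary analysis under ITT.

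The cost is SAP text and a somewhat lower NurOwn responder rate if untreated participants count as non-responders. If imputation becomes the primary rule, it moves from the sensitivity role that the protocol gives it. Power stays at 91% if 35% is the all-randomised rate; the 86% and 79% figures apply only if 35% was meant for treated participants.
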